8.2. Sample Size Determination

Since MDCI does not aim to test any specific hypothesis or answer any particular question, there is no statistical requirement to reach a specific number of samples and patients. It is expected to enroll 400 participants in this study.

8.3. Populations for Analyses

The following populations are defined:

Population	Description
Screened	All participants who sign the ICF
Enrolled	All participants who sign the ICF and meet inclusion/exclusion criteria
Ineligible for Treatment Trial	All participants who do not enrol onto a GSK treatment study
Randomized	NA
Safety	All participants who are enrolled and provided a tumor/blood sample

8.4. Statistical Analyses

Descriptive summary statistics of the key endpoints/markers (such as those considered for patient selection for various assets) will be tabulated and where relevant will be stratified by key baseline demographic and clinical characteristics.

Unsupervised clustering based on expression levels or mutation calls will be performed to identify cancer subtypes. The identified subtypes will be compared with subtypes found in previous research, such as TCGA (The Cancer Genome Atlas). For any phenotypic information of interest in the dataset, such as treatment outcome, the enrichment of phenotype in each subtype will be examined.

In addition, correlative and supervised analyses of molecular profiling data and other biomarker data in relation to specific phenotypes will be carried out via appropriate univariate (one marker at a time) analysis methods to assess and/or identify specific markers for further investigation. A variety of multivariate statistical and machine learning methods may also be carried out to identify combinatorial signatures and generate insights of potential use for patient selection/stratification or enrichment and other purposes in ongoing and upcoming clinical projects.

8.4.1. Safety Analyse(s)

Adverse event (AE) data will be summarized overall and stratified by appropriate baseline & clinical characteristics (examples: gender, tumor type/grade/antigen expression, etc.). These summaries will be categorized by frequency and proportion of total subjects. All AEs will be coded using the standard MedDRA.

8.4.2. Other Analyse(s)

Demographic and baseline characteristics will be summarized by tumor type (i.e. NSCLC, HNSCC, breast, ovarian, CRC); and by clinical characteristics of interest to be described in a subsequent analysis plan. Medical history; history of cancer diagnosis and treatment; past and current medical conditions will be listed.

Percentage of participants and investigators utilizing the portal systems.

Results from single and multi-marker *in vitro* diagnostic assays will be summarized by tissue (i.e., tumor, blood) and tumor type.

HLA-subtypes for HLA-A locus will be listed and summarized by tumor type. Separate summaries of HLA-A may be given by ethnicity.

Number of participants who successfully provided a tumor sample will be summarized by tumor type. Separate summaries may be given by baseline demographics such as age and ethnicity.

Number of participants who have been referred into a treatment trial will be summarized by tumor type and treatment trial. Separate summaries may be given by baseline demographics such as age and ethnicity.

Treatment Patterns: Anti-cancer treatments received will be summarized for all participants stratified by tumor type and by line of therapy.

Time to Next Treatment (TTNT): The length of time from the initiation of an anticancer therapy to the date that the next systemic anticancer therapy is initiated. When subsequent treatment is not received, patients should be censored at last known activity (e.g. last physician visit).

Time to Progression (TTP): The length of time from the date the patient initiates an anticancer therapy to the date that a progression event or death due to progression is reported by the physician in the patient chart.

Overall Survival (OS): This is defined as the interval of time between the date of treatment initiation and the date of death due to any cause. For participants who do not

die, time of death will be censored at the date of last contact. Death due to any cause will be included.

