Enrolled participants will be followed in two groups; (a) those enrolled onto a GSK clinical trial following Visit 3 and (b) those followed longitudinally, with disease reanalyzed at progression (Schedule of Activities Table 2). The total number of participants anticipated for this study is 400. Following consent, participants will have three initial study visits (further details on visits can be found in Schedule of Activities (SoA) and Section 4.1).

- **Visit 1:** Informed consent, review of medical history, targeted physical exam, information on Gather Share Know
- Visit 2: Biospecimen collection (e.g. tumor sample, blood), imaging
- **Visit 3:** Review results & trial matches with Physician, decide treatment options/treatment trial.

Note: Visit 1 and 2 may be combined, if appropriate, to reduce individual study visits. In the case that Visit 1 and 2 are combined, all corresponding samples must be collected per the SoA at this visit. In this scenario, following consent, all eligibility criteria should be confirmed prior to taking any Visit 2 assessments.

If a patient does not enroll onto a GSK study, or any other investigational study, the patient may remain under MDCI and be followed as per assessments on SoA Table 2.

Duration: It is expected that a majority of patients complete Visit 1 through Visit 3 in \leq 8 weeks; Participants who are followed longitudinally (SoA Table 2) may be followed for 2 years.

[figure not shown]
The study protocol will remain open until all designated GSK-sponsored impacted clinical trials (outlined in SRM) are closed to enrolment & all participants have completed this study or at the discretion of GSK.

Data Monitoring or Other Committee:

Study 213299 Translational Research Committee

This committee is composed of both internal and external disease-area experts. The objective of the Translational Research Committee for Study 213299 is to consult on trial design, development, and implementation of MDCI. Interim data will be reviewed to facilitate these efforts.

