Tumor Specimen ⁽³⁾		Х	1. Subsequent treatment and the associated clinical outcomes of interest will be collected for participants who do not enroll in a treatment protocol.	
Tumor Imaging	X ⁽⁴⁾	X (5)	Survival follow up will be conducted for participants who do not enroll in a treatment protocol.	
Vitals ⁽⁶⁾	Х	Х		
Review of AEs and SAEs that are related to study procedure(s) or lead to study withdrawal	Х	Х	3. If patient progresses while on Standard of Care (SoC), a tumor biopsy may be taken for re-analysis & potential referral to a treatment trial based on results. Image guidance preferred when feasible. Images from guidance procedure will be collected (see Section 7.2.3).	
Current anti-cancer therapies(1)	Х	Χ	4. Any imaging for standard of care tumor assessment by CT, MRI, PET, nuclear medicine,	
Survival Follow up ⁽²⁾	Х	Х	Xray, or photography that was conducted will be collected. Visit window for imaging ±8 weeks.	
			5. Imaging for tumor assessment conducted within 4 weeks prior to biopsy will be collected. Imaging conducted after biopsy is not required to be collected.	
			6. Blood Pressure, Pulse Rate and Temperature	

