A liquid biopsy (blood) will also be taken at Visit 2 to analyse circulating tumor DNA (ctDNA), and/or exosomes. In addition, participants will also provide mandatory blood samples for biomarker, validated clinical biomarker testing, and genetic research, as well as tumor imaging with CT/MRI. *HLA* genotype will be determined from whole blood DNA tested at a central laboratory.

CCI

WES data from the blood will also be used in conjunction with the SNP genotyping data to assess the effect of host genetic variation in one or more candidate genes or across the genome on cancer risk, progression, and response to cancer treatments. Details of testing and management of all samples can be found in the respective sections of the SRM and Study Laboratory Manual.

A subset of the generated results will be uploaded to the Physician Portal for review, followed by the Gather Share Know Participant Hub. Physicians will review the results with participants at Visit 3. If the results indicate eligibility for a specific clinical trial, appropriate referrals to those trials will be made by physician for further screening. Participants will only be provided access to their selected results through the Gather Share Know Participant Hub after they have received information on the significance/benefits of the testing. Training will be provided to all participants who consent on how to access and navigate the hub.

All participants will undergo a follow-up safety assessment for any serious adverse events (SAEs) assessed as related to protocol-mandated study procedures or leading to study withdrawal.

The study protocol will remain open until all designated GSK-sponsored impacted clinical trials (outlined in SRM) are closed to enrolment & all participants have completed this study or at the discretion of GSK.

Participants ineligible for Clinical trials

If a patient does not enroll onto a GSK study, or any other investigational study, , and who procced to receive Standard of Care (SoC) therapy, disease will continue to be monitored under MDCI following a separate Schedule of Activities (SoA) for longitudinal follow-up (Table 2). Accordingly, physicians will be asked to enter/ report all anticancer therapies received and the participant's survival status during follow-up, in order to characterize treatment patterns and survival outcomes respectively.

The following portals will be used for this study:

1. Gather Share Know Participant Hub

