5.1. Inclusion Criteria

Participants are eligible to be included in the study only if all of the following criteria apply:

Intended and Alternative Treatment Protocols

- 1. Participant is a candidate for molecular screening for a GSK precision therapeutic clinical study (the Intended Treatment Protocol) that is being conducted in parallel at or nearby the MDCI recruitment site.
- 2. Participant is willing to travel to a site recruiting for the intended GSK treatment protocol (or alternative treatment protocol), if feasible, and if, in the investigator's opinion, the patient would benefit from enrolment into the intended GSK treatment protocol at an alternative clinical site. See 213299 Study Reference Manual (SRM) for the most recently updated lists of recruiting treatment trials.

Type of Participant and Disease Characteristics

- 3. Confirmed advanced/metastatic diagnosis of solid malignancy, as described in the Intended Treatment Protocol, including but not limited to the following disease-areas: NSCLC, HNSCC, Breast, Ovarian, CRC
- 4. Life expectancy of >6 months.
- 5. Able to provide blood samples (see Section 7.7 for blood volume requirements).
- 6. Able to provide an archival formalin-fixed paraffin-embedded (FFPE) tumor specimen from a current lesion/most current setting. If an archival tumor specimen is not available, surplus tissue from standard of care procedures is acceptable before fresh biopsy may be obtained. If an archival block cannot be sent as per institutional guidance/policy, slides can be sent instead, refer to the respective sections of the SRM and Study Laboratory Manual for further details.

Sex

Female

Contraceptive use by women should be consistent with local regulations regarding the methods of contraception for those participating in clinical studies. Contraceptive use is a requirement for females as pregnancy is an exclusion for this study.

7. Female Participants:

- A female participant is eligible to participate if she is not pregnant or breastfeeding, and at least one of the following conditions applies:
 - Is not a woman of childbearing potential (WOCBP)
 OR
 - Is a WOCBP and using a contraceptive method that is highly effective (with a failure rate of <1% per year), preferably with low user dependency, as described in Appendix 4.
 - A WOCBP must have a negative highly sensitive pregnancy test (urine or serum) as required by local regulations) within 24 hours before tumor biopsy.

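### Time to next treatment (TTNT) censors patients who die before a next therapy, so a Kaplan-Meier summary would overstate the share who go on to one; exits to GSK treatment trials can pull the other way.

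*Protocol*

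**What the plan says.** Protocol 8.4.2 (Other Analyse(s)) defines TTNT as "The length of time from the initiation of an anticancer therapy to the date that the next systemic anticancer therapy is initiated". The censoring rule follows: "When subsequent treatment is not received, patients should be censored at last known activity (e.g. last physician visit". Death is not named as an event, a competing event or an exception.

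The neighbouring definitions do mention death. Overall survival says "Death due to any cause will be included", and time to progression ends when "a progression event or death due to progression is reported by the physician in the patient chart".

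Participants need a "Confirmed advanced/metastatic diagnosis of solid malignancy" (Protocol 5.1), and the Synopsis says "Participants who are followed longitudinally (SoA Table 2) may be followed for 2 years". On data, a footnote to Schedule of Activities Table 2 says "Survival follow up will be conducted for participants who do not enroll in a treatment protocol", and Protocol 4.1 asks physicians to "report all anticancer therapies received and the participant's survival status during follow-up".

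Three other places bear on who remains under observation:
- Protocol 4.2 counts a participant as having completed the study on signing consent to a GSK treatment protocol.
- Footnote 1 to Table 2 collects subsequent treatment for participants who do not enrol in a treatment protocol.
- Footnote 3 to Table 2 allows a new biopsy at progression, with possible referral to a treatment trial.

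The readable SAP text does not mention TTNT. SAP 4.7 declares no changes from the analyses planned in the protocol.

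**The concern.** A patient who has died cannot start a next therapy. Kaplan-Meier treats a censored patient as still able to have the event later, at the same rate as those still under observation. Applied to TTNT as defined, it shares out the dead patients' probability as though they would eventually be treated. The result answers how quickly next therapy would start if nobody died first, which is not what a reader of a treatment-pattern table expects.

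In advanced or metastatic disease followed for up to 2 years, some deaths before a next therapy are to be expected. Protocol 2.1 lists the description of treatment patterns and outcomes among the study's scientific aims. The overstatement would also grow with mortality, so tumour types with higher mortality would look more fully treated than they were.

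**Working it through.** The documents give no TTNT figure, so there is nothing to reproduce. The direction can be derived; the size can only be illustrated.

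**Direction.** At each next-therapy start, let d be the number starting and r the number still at risk. Then 1-KM rises by KM(t−) × d/r, where KM counts only next-therapy starts. Cumulative incidence rises by S(t−) × d/r, where S counts both next-therapy starts and deaths. Since S is never above KM, 1-KM is never below cumulative incidence. It is strictly higher once a death precedes a later next-therapy start.

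**Inputs.**
- Horizon of 24 months: the 2-year follow-up in the Synopsis.
- Median to next therapy of 8 months: assumed.
- Median to death without next therapy of 12, 24 or 36 months: assumed.
- Constant hazards: h1 = ln2/8 = 0.0866 and h2 = ln2/m2 per month, where m2 is the death median; H = h1 + h2.

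**Formulas.**
- 1-KM(t) = 1 − exp(−h1·t)
- Cumulative incidence (CIF)(t) = (h1/H)·[1 − exp(−H·t)]
- CIF median = −ln(1 − 0.5·H/h1)/H
- Median of next therapy or death = ln2/H

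**Results.** 1-KM is 1 − 2^(−12/8) = 64.6% at 12 months and 1 − 2^(−3) = 87.5% at 24 months. The KM median is 8.0 months whatever the death rate.

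| Death median (months) | H | CIF, 12 mo | CIF, 24 mo | Gap, 24 mo (points) | CIF median (months) | Next therapy or death, median (months) |
|---|---|---|---|---|---|---|
| 12 | 0.1444 | 49.4% | 58.1% | 29 | 12.4 | 4.8 |
| 24 | 0.1155 | 56.3% | 70.3% | 17 | 9.5 | 6.0 |
| 36 | 0.1059 | 58.9% | 75.4% | 12 | 8.9 | 6.5 |

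For the first row, h1/H = 0.60 and CIF(24) = 0.60 × (1 − e^(−3.466)) = 0.581.

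The KM median of 8.0 months is thus shorter than the time by which half of patients have really started a next therapy. It is longer than the median of next therapy or death, but that is a different endpoint and must be shorter.

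**Sensitivity.** With next-therapy medians of 6, 8 and 12 months and death medians of 12 to 36 months, the gap is 5 to 17 points at 12 months and 11 to 29 points at 24 months. With a death median of 120 months it is at most 4 points. Censoring deaths at the last 6-monthly visit instead of the death date raises the simulated 12-month 1-KM from 65% to 67–70%.

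**Exits to GSK trials.** Suppose, purely as an assumption, that 20% of next therapies are starts on a GSK protocol and that those participants are censored at consent. The observed next-therapy hazard falls to 0.8 × 0.0866 = 0.0693. Then 1-KM is 1 − exp(−0.0693 × 12) = 56% at 12 months and 81% at 24 months. With a death median of 36 months the true share is 59% and 75%, so the error changes sign between the two times. With a death median of 12 months the truth is 49% at 12 months, so 1-KM stays too high. In the 36-month case, cumulative incidence that handles deaths but still censors these exits gives 51% and 69%, which is too low at both times. Correcting for death alone is therefore not enough.

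**The case against.** The strongest reply is that the protocol names no estimator and tests no hypothesis. Censoring at death is correct for a cause-specific rate, and the error appears only if 1-KM is reported and read as the share treated. That stands, and it makes the point conditional. It does not remove it: a censoring rule has a purpose only in a time-to-event summary, and Kaplan-Meier is the common default.

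Second, a reader might infer that the reported TTNT proportion will be too high. The documents do not support that. Participants who leave on consenting to a GSK protocol may be lost just before a next therapy, which acts in the opposite direction. Only the death component has a known sign.

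Third, a reader might infer a contradiction from the way overall survival and time to progression count death. There is none. They are different endpoints, and time to progression counts only deaths due to progression.

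Fourth, the size is assumed. The 12-month death median is severe for a study requiring life expectancy above 6 months: it implies 1 − 2^(−6/12) = 29% dead by 6 months in the absence of a next therapy. The 29-point gap is the upper end of the illustration, not an expectation.

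Fifth, a reader might infer that the SAP dropped TTNT. Its numbering goes from 4.3 to 4.5, so relevant text may simply not be shown. Its silence is not evidence either way.

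Finally, Protocol 8.4.2 also summarises treatments by line of therapy, which gives some information on later treatment without this rule.

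**Conclusion.** The point holds in a limited, conditional form. As written, TTNT censors patients who die before a next therapy, and no readable text exempts them. If it is summarised by Kaplan-Meier, the death component overstates the share who start a next therapy and gives a median that is too short for that share. Under the assumed medians the 24-month overstatement is 12 to 29 points; where death first is rare it is 4 points or less. These sizes rest on constant hazards and medians that the documents do not supply. The net direction is open as long as the handling of GSK-trial exits is unstated. TTNT is a descriptive item among the other analyses, nothing is tested, and the primary endpoint is unaffected. Priority is low.

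**What to change.** First check whether SAP text not shown already covers TTNT. Wherever TTNT is reported, specify:

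- The cumulative incidence of starting the next systemic anticancer therapy, with death from any cause before it as a competing event.
- The start of treatment on a GSK protocol counts as a next therapy where the sponsor can supply the date. Otherwise that exit is a separate competing event, and the estimate is labelled as next therapy outside GSK trials.
- Only participants alive without a next therapy are censored, at last contact.
- If a median is wanted, time to next systemic therapy or death from any cause is reported as a separately labelled endpoint.

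Record the change in SAP 4.7. The SAP is the cheaper place, since Protocol 9.1.1 requires ethics approval for protocol amendments.

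The cost is some SAP wording and a standard competing-risks routine. Therapies and survival status are already collected for followed participants, and Protocol 7.5.6 requires death sections of the CRF for all deaths. The one possible extra item is the treatment start date from the sponsor's other trials; the labelled alternative avoids it. The downsides are that the cumulative-incidence median may not be reached (with both assumed medians at 12 months, 0.5 × (1 − 2^(−4)) = 47% have started by 24 months) and that the composite mixes treatment with death.

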8.5. Interim Analyses

Due to the continuous nature of this study, there is no interim analysis phase. Data will be continuously monitored and analysed in real-time during the course of the study.

8.6. Translational Research Committee

The Translational Research Committee (TRC) charter will describe the procedures related to TRC operations in greater detail.

8.7. Limitations

Patient population sampled may not be generalizable or comparable to participants who enrol in treatment protocols.

9. SUPPORTING DOCUMENTATION AND OPERATIONAL CONSIDERATIONS

9.1. Appendix 1: Regulatory, Ethical, and Study Oversight Considerations

9.1.1. Regulatory and Ethical Considerations

- This study will be conducted in accordance with the protocol and with:
 - Consensus ethical principles derived from international guidelines including the Declaration of Helsinki and Council for International Organizations of Medical Sciences (CIOMS) International Ethical Guidelines
 - Applicable ICH Good Clinical Practice (GCP) Guidelines
 - Applicable laws and regulations
- The protocol, protocol amendments, ICF, Investigator Brochure, and other relevant documents (e.g., advertisements) must be submitted to an IRB/IEC by the investigator and reviewed and approved by the IRB/IEC before the study is initiated.
- Any amendments to the protocol will require IEC/IRB approval before implementation of changes made to the study design, except for changes necessary to eliminate an immediate hazard to study participants.
- The investigator will be responsible for the following:
 - Providing written summaries of the status of the study to the IRB/IEC annually or more frequently in accordance with the requirements, policies, and procedures established by the IRB/EC
 - Notifying the IRB/IEC of SAE or other significant safety findings as required by IRB/IEC procedures
 - Providing oversight of the conduct of the study at the site and adherence to requirements of 21 CFR, ICH guidelines, the IRB/IEC, European regulation 536/2014 for clinical studies (if applicable), and all other applicable local regulations

9.1.2. Financial Disclosure

Investigators and sub-investigators will provide the sponsor with sufficient, accurate financial information as requested to allow the sponsor to submit complete and accurate financial certification or disclosure statements to the appropriate regulatory authorities. Investigators are responsible for providing information on financial interests during the course of the study and for 1 year after completion of the study.

